Participants assigned to receive WASABI will complete at least 3 EMA sessions per week, 1 hour of digitally delivered Cognitive Behavioral Group Therapy (dCBGT) per week, and weekly cognitive biases assessments and self-reports for 12 weeks. During the intervention, these participants will also have daily access to 1:1 and group chat Instant Messaging (IM) and may have weekly electronic check-ins with Site Study personnel (as needed). Participants in the control condition will be asked to attend 1 hour of digitally delivered Cognitive Behavioral Group Therapy (dCBGT) per week for 12 weeks and may have weekly electronic check-ins with Site Study personnel (as needed).

For each arm, as soon as 3-6 participants have completed the baseline assessments and randomization, a cohort will be assembled. The Study Coordinator will meet with the participants to orient them to the study platforms and the WASABI Clinician will meet with each participant individually for a brief introduction and orientation prior to the 12-week intervention and will review of the *Procedures and Guidelines to Group Therapy*. The WASABI Coordinator and/or Clinician will create a virtual support group open only to cohort participants. The WASABI Clinician will explain her role, make group introductions, and will invite participants to attend weekly 1-hour group sessions (dCBGT+ WASABI or dCBGT only, depending on the treatment arm). For the treatment group (dCBGT + WASABI), between group sessions, the WASABI Clinician will spend approximately 30 min/day keeping the chat active during work hours, checking it approximately 3 times a day and may respond to messages participants leave, as appropriate. The WASABI Coordinator will be included in the support group chat and may monitor the chat content, and may be active in the chat in the absence of the WASABI Clinician.

Participants will be re-evaluated again at the expected time of completion, immediately following the 12-week intervention, to evaluate changes in performance. Finally, participants will be asked to fill out an online exit survey to rate enjoyment, usability, perceived benefits, and ease of fit into schedule.

The protocol will be conducted in accordance with the protocol submitted to and approved by the reviewing Institutional Review Board and approval will be obtained prior to implementation.

Study Population

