Experimental Treatment Intervention (dCBGT+WASABI): The Experimental Treatment Intervention is a mobile-delivered and clinically-supervised adjunct to treatment composed of three primary treatment tools. Participants will be asked to 1) attend 12 weekly, 1-hour, group dCBGT sessions and complete "homework" associated with traditional dCBGT; 2) complete 3 EMA sessions per week, weekly standardized SA self-report, and weekly cognitive assessments; 3) use IM for 1:1 and group conversations. At the beginning of each treatment cohort, the WASABI Clinician will create a group text open only to cohort participants, explain their role, and make introductions. Between group sessions, the WASABI Clinician will spend approximately 30 min/day keeping the chat active during work hours, checking it approximately 3 times a day and responding to any messages participants leave, as appropriate. The WASABI Clinician will also receive notifications whenever the WASABI algorithm detects SA symptom exacerbation, and engage participants in synchronous or asynchronous IM. In absence of alerts, the WASABI Clinician will monitor the WASABI dashboard the day before each dCBGT session to customize the delivery of targeted content during the videocall.

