- Site Clinical Assessor will serve as the blinded psychometrician and clinical rater. She will conduct eligibility and clinical assessments with participants and will be blinded to their randomization assignment. S/he may assist with conducting preliminary screening interviews with participants and conducting consent discussions, as needed. The assessor may assist with connecting with different community organizations, clinics, schools or other sources of recruitment.
- Site WASABI Clinician will lead the group CBT sessions, for treatment and control. She will monitor the Google Meets forum and may be responsible for removing and/or discussing the Google Meet chat content with the appropriate team members, WASABI Clinician(s) and the Posit Science research team. For participants assigned to the WASABI treatment, she will manage the clinician dashboard, and engage participants in ecologically valid interactions. The WASABI Clinician may assist with connecting with different community organizations, clinics, schools or other sources of recruitment.
- Volunteers may be recruited to assist Study Coordinator with study activities, including, but not limited to, recruiting, contacting and conducting a preliminary screening of participants.
- Site Regulatory Study Monitor may be required to access study documents and data capture systems to conduct study monitoring visits to ensure adherence to institutional requirements.

Blinding

Un-blinded Site Roles: At each site, *WASABI Clinicians* are un-blinded in order to provide lead dCBGT sessions and support for participants using their assigned programs. They will be distinct from staff administering and scoring follow-up assessments. Additionally, designated personnel that are un-blinded may not participate in the assessment and evaluation at follow-up assessments (V3) of study participants.

Blinded Site Roles: All site staff responsible for the administration and scoring of participant assessments visits conducted after randomization will remain blinded to participant treatment. Site Principal Investigators will be required to complete a Delegation of Authority Form, indicating which activities individual site research team members will be authorized to complete. Site Principal Investigator will also remain blinded.

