For feasibility, we relied on descriptive statistics. For preliminary efficacy, in smaller sample sizes like ours, there is a greater likelihood that there will be larger differences at baseline between groups simply due to sampling error. Groups were compared on all baseline measures using Mann-Whitney U tests (for ordinal and continuous variables) or Pearson chi-square/Fisher's exact test (for categorical variables). To test whether groups differed in change over time, data were analyzed via linear mixed-effects models. Mixed-effects models are ideal for the analysis of longitudinal data, due to the fact that it tolerates missing observations—assuming that it is missing at random (MAR). First, simple growth models (change from baseline to post) were conducted to examine change over time (for all participants). Because complete case analyses have been shown to provide biased estimates in the presence of missing data (Enders, 2010), data were then modeled using the intent-to-treat (ITT) framework, in which all randomized subjects are included in the analysis, and missing data were handled via Full Information Maximum Likelihood (FIML). This method for handling missing data is considered a gold standard approach, as it gives relatively unbiased estimates (Enders, 2010), and is the standard for the analysis of randomized trials. For all models, fixed effects of time, group, and group x time interaction were included; a random intercept of subject was used. Kenward-Roger degrees of freedom were used due to the small sample size; statistical significance was evaluated at a two-sided alpha of $p = 0.05$; however, null hypothesis testing was de-emphasized given the small sample size of the control group ($n = 8$). We emphasize the effect size (Cohen's d) instead. Although various estimates of effect size exist for LMM, we chose a simplified version, defined as:

$$\frac{(\Delta_{(dCBT+WASABI)} - \Delta_{(dCBT)})}{\sigma_{pre}}$$

Where Δ refers to slope (i.e., change from baseline to post-intervention) and σ_{pre} refers to the pooled baseline standard deviation. Thus, values of d refer to change in standard deviation units from baseline.

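### Therapy runs in arm-specific cohorts of 3-6, but the efficacy model has no cohort term: if change correlates within cohorts, the secondary between-arm p-values would be too small

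*SAP*

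**What the plan says.** **Delivery.** Protocol, General Study Design: "For each arm, as soon as 3-6 participants have completed the baseline assessments and randomization, a cohort will be assembled". Each cohort then has its own weekly one-hour sessions for 12 weeks. In the experimental arm there is also a shared chat: "the WASABI Clinician will create a group text open only to cohort participants" (Protocol, Experimental Treatment Intervention). Controls are not asked to use the chat application (Protocol, Application Security). The same clinician role serves both arms: "Site WASABI Clinician will lead the group CBT sessions, for treatment and control" (Protocol, Study Personnel).

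**Model.** SAP section 2: "fixed effects of time, group, and group x time interaction were included", and "a random intercept of subject was used". Also, "Kenward-Roger degrees of freedom were used due to the small sample size". The protocol's Data Analysis section says only that a linear mixed model will be used. Neither document has a cohort effect, a cluster-robust variance, an ICC or a design effect.

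**Use of the results.** The efficacy scales are secondary; the primary outcomes are feasibility measures summarised descriptively. The SAP plays down hypothesis testing and puts Cohen's d first. It nevertheless keeps p<0.05 as its criterion and calls p<0.1 a trend. The protocol's Sample Size Justification goes further: p<0.05 is to support a statement that the intervention improves social anxiety. The same section and Data Analysis say the data will be used to power the pivotal Phase II trial.

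**The concern.** Members of a cohort share sessions, practise exposure on one another and, in the WASABI arm, share a chat and session content tailored to that cohort's own momentary-assessment data. It is plausible that their changes resemble each other. Cohort is nested in arm, so any cohort-to-cohort variation in change feeds directly into the between-arm contrast. A model whose only random effect is the subject counts that variation as if it came from independent people. Kenward-Roger does not help, because it adjusts for the levels in the model and not for one left out.

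At stake are the p-values and trend labels on the secondary outcomes, and the precision credited to estimates that feed Phase II sizing.

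**Working it through.** **Inputs.** Planned completers 12 v 12 (Protocol, General Study Design); a control arm of 8 is mentioned in SAP section 2, so 12 v 8 is also shown. Cohort size m = 3 to 6 (Protocol). Two-sided alpha 0.05 and trend threshold 0.1 (SAP). The cohort ICC of change is **assumed**, at 0 to 0.20.

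**Step 1: number of cohorts.** Twelve people make 12/6 = 2 to 12/3 = 4 cohorts. Eight people in cohorts of 3-6 can only make two. The contrast therefore rests on 4-8 cohorts (12 v 12) or 4-6 (12 v 8), while the model uses 12+12-2 = 22 or 12+8-2 = 18 degrees of freedom.

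**Step 2: the plan's own figure.** With two time points and complete data, the group-by-time t in a subject-random-intercept model equals the two-sample t on change scores (confirmed on three simulated data sets). At ICC 0, simulation with 200,000 runs per scenario gave a rejection rate of 0.049-0.051, so the nominal 5% is reproduced.

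**Step 3: add a cohort effect on change.** With equal cohorts, N people, k cohorts and unit variance:

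- design effect DEFF = 1 + (m-1) x ICC, by which the true variance of the contrast rises;
- the pooled variance the model estimates has expectation [DEFF x (k-2) + (1-ICC) x (N-k)] / (N-2), which is below 1 when ICC > 0.

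Example, 12 v 12, m = 6, k = 4, ICC = 0.20: DEFF = 1 + 5 x 0.20 = 2.00. The model's variance has expectation (2.00 x 2 + 0.80 x 20)/22 = 20/22 = 0.909. True over model SE = sqrt(2.00/0.909) = 1.48. The simulation gave the same.

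Actual rejection rate of a nominal 5% test with no true effect:

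| Layout | ICC 0.01 | ICC 0.05 | ICC 0.10 | ICC 0.20 | True/model SE at 0.20 |
|---|---|---|---|---|---|
| 12 v 12, m = 3 | 5.2% | 6.2% | 7.5% | 10.1% | 1.21 |
| 12 v 12, m = 4 | 5.4% | 6.8% | 8.6% | 12.6% | 1.30 |
| 12 v 12, m = 6 | 5.6% | 8.1% | 11.3% | 17.8% | 1.48 |
| 12 v 8, m = 4 | 5.3% | 6.9% | 8.6% | 12.7% | 1.31 |

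For 12 v 12, the p<0.1 trend rule has an actual error rate of 12-26% over ICC 0.05-0.20.

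**Step 4: what a correction can do.**

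- *Analysis at cohort level* brings the error back to 4.9-5.1%. Degrees of freedom fall from 22 to k-2 = 6, 4 or 2 for m = 3, 4, 6, and the critical t rises from 2.07 to 2.45, 2.78 or 4.30. For 12 v 8 with m = 4, they fall from 18 to 3 and the critical t rises from 2.10 to 3.18.
- *A cohort intercept constant over time* cancels out of change. Adding one left the group-by-time t essentially unchanged.
- *Multiplying the model SE by sqrt(DEFF)* corrects most of the problem but not all, because the model SE is itself too low. At ICC 0.20 the multiplier is 1.18-1.41 where 1.21-1.48 is needed, and the error after correction is about 5.4-6.2%.

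**The case against.** The strongest reply is that little depends on these tests. Efficacy is secondary, the protocol concedes that the trial lacks power for an augmentation effect, and the SAP emphasises Cohen's d. That d is a difference in change over the pooled baseline SD, and clustering that arises after baseline does not bias its point estimate. All of this stands and limits the weight of the point. It does not remove it, because both documents still attach conclusions to p-values.

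Second, the ICC is unknown. This also stands: at 0.01 the effect is slight and at zero there is none. But the SAP's model implies zero without saying so or giving a reason.

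Third, one clinician role leads groups in both arms, so a clinician effect is not wholly confounded with arm. That removes part of one source of clustering. Group process remains, and the protocol allows for alternate or back-up clinicians.

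Fourth, a cohort variance can hardly be estimated from so few cohorts. True, and this is why the fix below does not rest on it.

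A reader might infer more than the documents support:

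- *That the standard errors are definitely too small.* This needs a positive within-cohort correlation, which the documents neither give nor rule out.
- *That the planned confidence intervals are too narrow.* The SAP specifies none for the between-arm effect.
- *That Phase II will be sized without a design effect.* The documents describe no sizing method, so the omission is possible and not established.

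**Conclusion.** The gap is real and its consequence is conditional. The efficacy model leaves out a level that the design creates. If change is positively correlated within cohorts, the type I error of the secondary group-by-time tests is about 6-8%, 7-11% or 10-18% at ICC 0.05, 0.10 or 0.20. The upper ends need every cohort to have six members. These figures assume complete data, two time points, equal cohorts and the same ICC in both arms; the last may fail, since only WASABI cohorts share a chat. The primary feasibility results and the point estimate of d stand as planned. This warrants a sensitivity analysis and more careful wording. It does not invalidate the trial.

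**What to change.** 1. Record a cohort identifier for every participant.
2. Keep the subject-level model. For each secondary between-arm effect, add a confidence interval and p-value recalculated at assumed cohort ICCs of 0.01, 0.05, 0.10 and 0.20, with the model SE multiplied by sqrt(1 + (m-1) x ICC). State that the ICCs are assumptions and that the multiplier slightly under-corrects at 0.20.
3. As a supportive analysis only, fit a cohort-by-time random effect (not a time-constant cohort intercept) with Kenward-Roger degrees of freedom. Say in advance that its variance will be poorly estimated and may come out at zero, in which case the result reverts to the subject-level one.
4. Word any p<0.05 or p<0.1 statement, including the one in the protocol's Sample Size Justification, as conditional on this sensitivity analysis.
5. If Phase II keeps group delivery, carry a design effect into its sample size. Over cohorts of 3-6 and ICC 0.05-0.20 it runs from 1 + 2 x 0.05 = 1.10 to 1 + 5 x 0.20 = 2.00.

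The cost is a little extra analysis and wider intervals. Recruitment, treatment and assessments do not change.

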Once three participants are deemed eligible and enrolled in the pilot trial, they will be scheduled for three focus group sessions that could occur in-person or remotely, to be completed over the course of approximately 2-weeks. Each session will last approximately 1 hour and will be facilitated by the study clinician(s). After feedback from the focus group sessions is implemented into the app and dashboard design, the three adolescents will be granted access to the WASABI app and engage in a 2-week trial period, during which the predictive ability of the algorithm will be validated by the WASABI clinician, who will verify via 1:1 remote videocalls the actual presence of clinically-significant social anxiety whenever the WASABI clinician receives an alert. Additionally, this trial period will ensure that WASABI EMA data are timely evaluated by the clinician on the dashboard and meaningfully orient the delivery of individualized IM and weekly dCBGT content. At the end of the 2-week trial period of WASABI, participants will be asked to rate their enjoyment, ease of use, product quality, and perceived usefulness in a 1:1 user interview. Finally, we will submit these data from the trial period to our consultant to confirm that WASABI is suitable for the feasibility trial.

General Study Design

We will employ a standard prospective, parallel arm, double-blind, randomized, controlled clinical trial to assess the safety and efficacy of WASABI in adolescents with Social Anxiety (SA), and evaluate its potential in augmenting the efficacy of dCBGT in improving social

anxiety, social skills and social functioning. We will randomize adolescents with SA (ages 14-18) to receive either 12 weeks of dCBGT+WASABI or dCBGT only.

Approximately 32 participants will be consented to ensure the successful completion of 24 participants (12 participants per treatment arm). A diagnostic interview will be performed to determine eligibility. Following inclusion and enrollment, participants will complete a set of assessments prior to the intervention to establish their baseline performance. Participants will then be randomized to dCBGT+WASABI or dCBGT only and spend up to 12 weeks engaged in their assigned intervention.

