We hypothesize that the innovative features of WASABI will improve the quality of treatment delivery and facilitate the generalization of trained skills into real-world settings. The measures collected to determine the efficacy of the program for this trial are clinical ratings of anxiety and social anxiety symptoms (LSAS-CA), self-report inventories of social anxiety symptoms (SPAI), broad measures of anxiety (MASC-2), self-report inventories of social skills (SSQ), and self-report inventories of social functioning (ASSES). To test this hypothesis, we will use a linear mixed model approach. We will first compare treatment and active control groups in the ITT population to determine if any differences in baseline demographic, characterization, outcomes variables, or total program use time remain after the randomization process. Any such factors that show trend level significant differences ($p < 0.1$) will be noted and used as covariates in the linear mixed model analysis. The criterion for statistical significance is $p < 0.05$. Results with $p < 0.1$ will be described as trends.

Performance on the attention bias and interpretation bias assessments will be modeled longitudinally to examine if these measures can serve as potential moderators and mediators. To test if the attenuation of attention and interpretation biases mediates improvements in outcome measures, we will use repeated-measures linear mixed modeling to test in the active group the effects of WASABI on LSAS-CA, SPAI, SSQ and ASSES, and then model outcomes as a function of performance improvements on the attention bias and interpretation bias assessments.

Because we are interested in examining the ecological validity of WASABI, we will not restrict the analyses only to participants who adhered to all intervention requirements. Within-group effect sizes (Cohen's d) will be computed using the mean change scores (post-intervention minus baseline) and the change score SDs.

These measures will be analyzed to power the pivotal study proposed for Phase II. For the FDA, we will collect data documenting that WASABI meets its design requirements when used in the field by clinicians and patients, and that clinicians deem its risk/benefit ratio as acceptable and view it as adequate/appropriate for the target population.

Data Management

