Statistical Analysis Plan

WASABI: Wiring Adolescents with Social Anxiety Via Behavioral Interventions

Protocol Number: PSC-1016-19

NCT03990870

Document Date: July 8, 2019

(1) ANALYSIS POPULATIONS

There are three *a priori* defined analysis populations, including a primary analysis population (i), a secondary analysis population designed to compare effect sizes in populations with no missing data (ii) and a population who completed all training visits (iii)

- i. *Intent to Treat (ITT) population:* This is the *a priori* primary analysis population, defined as including all randomized participants who attended at least one group video call.
- ii. *Intent to Treat (ITT) Fully-Evaluable (FE) population:* This is a secondary analysis population, defined as including all members of the ITT population that complete a post-intervention visit. Note that a participant may complete a specific visit but have missing data for a test in which case the participant is in the overall FE population but does not contribute data to the FE population for that visit, e.g., the number of evaluable cases for a specific test on a specific visit may be smaller than the FE population for that visit because of missing data.
- iii. *Intent to Treat (ITT) Completers (C) population:* This is a secondary analysis population, defined as including all members of the ITT-FE population who complete all intervention sessions. Note that the C populations are strict subsets of the FE populations; a person who completes the target number of videocalls but does not complete the evaluation visit is not a member of the C population.

(2) STATISTICAL PLAN

Feasibility

The Phase I data analysis plan *a priori* defines a primary intent-to-treat (ITT) population, a set of secondary evaluation populations, a set of primary outcome measures, a set of secondary outcome measures, a set of potential mediators/moderators, a single primary evaluation time point, a criterion for statistical significance, and a statistical analysis methodology for secondary outcomes.

- The primary ITT population is defined as all participants who attend one dCBGT video call. Note that this includes all randomized participants except those who drop/withdraw post-randomization and pre-training.

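### The SAP is dated July 2019 and labelled a priori, yet it plays down testing because of a control group of 8 found in no plan; that choice is post hoc, and two others cannot be shown to be pre-specified

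*SAP*

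**What the plan says.** **SAP, title block and section (1).** The title block gives "Document Date: July 8, 2019". Section (1) describes three analysis populations as defined a priori.

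**SAP, section (2), Feasibility.** The section opens with "The Phase I data analysis plan *a priori* defines a primary intent-to-treat (ITT) population" and extends that description to the outcome sets, the evaluation time point, the significance criterion and the method for secondary outcomes. The analysis of the primary feasibility measures is then announced in the future tense. Usability ratings and secondary outcomes, however, are described as already obtained, and the final paragraph describes the baseline comparisons, mixed models and degrees-of-freedom method as already carried out. That paragraph states that "null hypothesis testing was de-emphasized given the small sample size of the control group", with n = 8 in brackets, and that the effect size is emphasised instead.

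**Protocol, General Study Design.** About 32 participants are to be consented "to ensure the successful completion of 24 participants (12 participants per treatment arm").

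**Protocol, Data Analysis.** Baseline factors that differ between arms at p < 0.1 "will be noted and used as covariates in the linear mixed model analysis". Effect sizes are within-group, using the SD of the change scores; Sample Size Justification says the same.

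**Protocol, Screening Procedures.** Treatment with anxiety or psychiatric medication is to enter every statistical analysis as a covariate.

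**The concern.** A dated, a priori analysis plan tells the reader that its choices could not have been shaped by the data. Here the document takes one decision from a group size that neither plan contains, and much of it reads as a report of finished work. Its date and its label therefore cannot both describe the text as it stands.

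The efficacy results are secondary, but they have a use: Sample Size Justification and Data Analysis in the protocol both say that the data will be used to power the Phase II pivotal trial. Whoever plans that trial needs to know which effect size and which model were planned and which were chosen later. Sample Size Justification also treats p < 0.05 as support for an efficacy statement, so a later reduction in the role of testing changes how the results are to be read.

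**Working it through.** The question is one of timing and wording, so most of the check sets the texts side by side.

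**1. Is 8 a planned number?** The protocol's planned arm size is "12 participants per treatment arm", with 24 completers from about 32 consented. The SAP itself uses 12 as the treatment-arm denominator when it sets its programme-completion target. The 8 in that target counts completers in the treatment arm and is not a control-group size. Nothing in either document plans 8 controls.

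- Shortfall: 12 − 8 = 4; 4/12 = 33%.
- The implied attrition, 1 − 24/32 = 25%, is already allowed for in the step from 32 to 24, so it does not turn 12 into 8.

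The natural reading is that 8 is the achieved size. The SAP does not use that word, so this is an inference.

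**2. What depends on 8?** The SAP links the number to one decision, the lower weight on hypothesis tests, and the next sentence presents the emphasis on d as its replacement. Both therefore depend on recruitment. The SAP links neither the formula for d nor the list of model terms to the number 8.

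**3. Where else do the SAP's efficacy choices differ from the protocol?**

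| Item | Protocol | SAP, section (2) |
|---|---|---|
| Covariates | Baseline factors with p < 0.1 (Data Analysis); medication treatment in all analyses (Screening Procedures) | Time, group, their interaction and a random subject intercept, stated for all models; no covariates listed |
| Cohen's d | Within-group mean change / SD of change | Between-arm difference in change / pooled baseline SD |

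**4. Does the choice of denominator matter?** With equal SDs before and after treatment and correlation r between the two measurements, SD(change) / SD(baseline) = √(2(1 − r)). The documents give no r, so a range is assumed:

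- r = 0.3: √1.4 = 1.18
- r = 0.5: √1.0 = 1.00
- r = 0.7: √0.6 = 0.77
- r = 0.9: √0.2 = 0.45

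For the same mean change, d over the baseline SD equals d over the change-score SD multiplied by this ratio. The two agree only at r = 0.5, and at r = 0.9 the baseline-SD version is less than half the other. The numerators differ too, one being a change within an arm and the other a contrast between arms.

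**5. What is prospective in the protocol?** Data Analysis states the linear mixed model, the 0.05 criterion, the p < 0.1 trend label and the measures LSAS-CA, MASC-2, SSQ and ASSES in the future tense. These do not rely on the SAP's date.

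**The case against.** The other side has a good case on several points.

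- **Playing down tests is sensible and openly stated.** The protocol already says that 24 participants give too little power, and the SAP still evaluates significance at a two-sided 0.05. This stands as a defence of the choice but not of the a priori label, because the reason given is a control size no plan contains.
- **The SAP's d may fill a gap.** The protocol seeks a between-group difference but defines only a within-group d, and the SAP does not say that its formula replaces the protocol's. This stands, which is why the point is that pre-specification cannot be shown, not that a planned measure was abandoned.
- **Listing core terms does not exclude covariates.** The SAP keeps the baseline comparisons, the first step of the protocol's p < 0.1 rule. That rule is conditional, so silence about it could be an omission. The medication covariate is unconditional, however, and it is missing from a list given for all models.
- **The efficacy outcomes are secondary.** The primary measures are feasibility measures analysed descriptively. This limits the consequence.

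Three stronger readings are tempting, and the documents support none of them.

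- A reader might infer that the whole SAP is post hoc. Step 5 of the working shows otherwise.
- A reader might infer that the choices were made after outcomes were seen. The past tense shows when the text was written, not when a choice was made, and nothing states who had access to outcome data.
- A reader might want a figure for lost precision. The treatment-arm size is not stated, so any such figure is assumed: relative to 12 v 12 the standard error rises by √((1/12 + 1/8)/(2/12)) = 1.118 with 12 treated, but by √((1/16 + 1/8)/(2/12)) = 1.061 with 16. Neither measures loss of pre-specification.

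Nor can the protocol simply be taken as the earlier benchmark. Its descriptions of the group therapy in both arms allow for adjustments during COVID-19, so that text is later than July 2019. A difference between the two documents does not by itself show which one changed.

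**Conclusion.** The point holds in limited form. The lower weight on testing, with the matching emphasis on d, is post hoc on its face, and the SAP text was written or revised after its stated date. The covariate-free model and the between-arm, baseline-SD d differ from the protocol and cannot be shown to be pre-specified; whether they followed accrual is unknown.

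In size, this is one choice that cannot be a priori and two without dated support, in a trial whose control group is 4 of 12 (33%) below plan. Depending on r, the change of denominator alone could rescale d by a factor of 0.45 to 1.18.

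The conclusion assumes that 8 is the achieved control size. The protocol's version date does not appear in the text reviewed, where title pages are left out, so the order of the two documents is open.

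**What to change.** 1. Issue the SAP text with its true finalisation date, and state where that date falls relative to database lock, unblinding and access to outcome data.
2. Give the date of the protocol version that fixed each analysis choice.
3. Remove the a priori description from the n = 8-driven reduction of testing and the emphasis on d, and label both post hoc.
4. Label the between-arm, baseline-SD d and the covariate-free model post hoc unless an earlier dated version contains them.
5. Report the protocol-specified covariate-adjusted model and within-group d alongside the SAP's versions.

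The cost is one extra model per outcome, some re-dating and labelling, and a weaker claim of pre-specification. No new data are needed.
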